### ***Treatment of Ipilimumab-Related Isolated Drug Fever***

In the event of isolated drug fever, the investigator must use clinical judgment to determine if the fever is related to the ipilimumab or to an infectious etiology. If a patient experiences isolated drug fever, for the next dose, pre-treatment with acetaminophen or non-steroidal anti-inflammatory agent (investigator discretion) should be instituted and a repeated antipyretic dose at 6 and 12 hours after ipilimumab infusion, should be administered. The infusion rate will remain unchanged for future doses. If a patient experiences recurrent isolated drug fever following premedication and post dosing with an appropriate antipyretic, the infusion rate for subsequent dosing should be decreased to 50% of the previous rate. If fever recurs following infusion rate change, the investigator should assess the patient's level of discomfort with the event and use clinical judgment to determine if the patient should receive further ipilimumab.

### **Monitoring and Management of Immune-mediated Adverse Reactions**

#### **Immune-mediated Enterocolitis**

Patients will be monitored for signs and symptoms of enterocolitis (such as diarrhea, abdominal pain, mucus or blood in stool, with or without fever) and of bowel perforation (such as peritoneal signs and ileus). In symptomatic patients,

rule out infectious etiologies and consider endoscopic evaluation for persistent or severe symptoms.

Permanently discontinue ipilimumab in patients with severe enterocolitis and initiate systemic corticosteroids at a dose of 1 to 2 mg/kg/day of prednisone or equivalent. Upon improvement to Grade 1 or less, initiate corticosteroid taper and continue to taper over at least one month. In clinical trials, rapid corticosteroid tapering resulted in recurrence or worsening symptoms of enterocolitis in some patients. For steroid-refractory colitis infliximab 5 mg/kg IV or cyclosporine 2 mg/kg IV for 7 days are recommended.

Withhold ipilimumab dosing for moderate enterocolitis; administer anti-diarrheal treatment and, if persistent for more than one week, initiate systemic corticosteroids at a dose of 0.5 mg/kg/day prednisone or equivalent.

### **Immune-mediated Hepatitis**

Monitor liver function tests (hepatic transaminase and bilirubin levels) and assess patients for signs and symptoms of hepatotoxicity before each dose of ipilimumab. In patients with hepatotoxicity, rule out infectious or malignant causes and increase frequency of liver function test monitoring until resolution.

Permanently discontinue ipilimumab in patients with Grade 3–5 hepatotoxicity and administer systemic corticosteroids at a dose of 1 to 2 mg/kg/day of prednisone or equivalent. When liver function tests show sustained improvement or return to baseline, initiate corticosteroid tapering and continue to taper over 1 month. Across the clinical development program for ipilimumab, mycophenolate treatment has been administered in patients who have persistent severe hepatitis despite high-dose corticosteroids. Withhold ipilimumab in patients with Grade 2 hepatotoxicity.

### **Immune-mediated Dermatitis**

Monitor patients for signs and symptoms of dermatitis such as rash and pruritus. Unless an alternate etiology has been identified, signs or symptoms of dermatitis should be considered immune-mediated.

Permanently discontinue ipilimumab in patients with Stevens-Johnson syndrome, toxic epidermal necrolysis, or rash complicated by full thickness dermal ulceration, or necrotic, bullous, or hemorrhagic manifestations. Administer systemic corticosteroids at a dose of 1 to 2 mg/kg/day of prednisone or equivalent. When dermatitis is controlled, corticosteroid tapering should occur over a period of at

least 1 month. Withhold ipilimumab dosing in patients with moderate to severe signs and symptoms.

For mild to moderate dermatitis, such as localized rash and pruritus, treat symptomatically. Administer topical or systemic corticosteroids if there is no improvement of symptoms within 1 week.

### **Immune-mediated Neuropathies**

Monitor for symptoms of motor or sensory neuropathy such as unilateral or bilateral weakness, sensory alterations, or paresthesia. Permanently discontinue ipilimumab in patients with severe neuropathy (interfering with daily activities) such as Guillain-Barré-like syndromes. Institute medical intervention as appropriate for management of severe neuropathy. Consider initiation of systemic corticosteroids at a dose of 1 to 2 mg/kg/day prednisone or equivalent for severe neuropathies. Withhold ipilimumab dosing in patients with moderate neuropathy (not interfering with daily activities).

### **Immune-mediated Endocrinopathies**

Monitor patients for clinical signs and symptoms of hypophysitis, adrenal insufficiency (including adrenal crisis), and hyper- or hypothyroidism. Patients may present with fatigue, headache, mental status changes, abdominal pain, unusual bowel habits, and hypotension, or nonspecific symptoms which may resemble other causes such as brain metastasis or underlying disease. Unless an alternate etiology has been identified, signs or symptoms of endocrinopathies should be considered immune-mediated.

Monitor thyroid function tests and clinical chemistries at the start of treatment, before each dose, and as clinically indicated based on symptoms. In a limited number of patients, hypophysitis was diagnosed by imaging studies through enlargement of the pituitary gland. Withhold ipilimumab dosing in symptomatic patients. Initiate systemic corticosteroids at a dose of 1 to 2 mg/kg/day of prednisone or equivalent, and initiate appropriate hormone replacement therapy.

### **Other Immune-mediated Adverse Reactions, Including Ocular Manifestations**

The following clinically significant immune-mediated adverse reactions were seen in less than 1% of ipilimumab-treated patients in previous studies: nephritis, pneumonitis, meningitis, pericarditis, uveitis, iritis, and hemolytic anemia.

Across the clinical development program for ipilimumab, the following likely immune-mediated adverse reactions were also reported with less than 1% incidence: myocarditis, angiopathy, temporal arteritis, vasculitis, polymyalgia rheumatica, conjunctivitis, blepharitis, episcleritis, scleritis, leukocytoclastic

vasculitis, erythema multiforme, psoriasis, pancreatitis, arthritis, and autoimmune thyroiditis.

Permanently discontinue ipilimumab for clinically significant or severe immune-mediated adverse reactions. Initiate systemic corticosteroids at a dose of 1 to 2 mg/kg/day prednisone or equivalent for severe immune-mediated adverse reactions.

Administer corticosteroid eye drops to patients who develop uveitis, iritis, or episcleritis. Permanently discontinue ipilimumab for immune-mediated ocular disease that is unresponsive to local immunosuppressive therapy.

### ***Liver Function Test (LFT) Assessments Required Before Administration of Ipilimumab***

Liver function tests (AST, ALT, T. bilirubin) will be evaluated for every subject prior to administration of ipilimumab. Blood samples must be collected and analyzed at local or central labs within 3 days prior to dosing. LFT results must be reviewed by the principal investigator (or designee) to meet dosing criteria specifications:  $\leq 2.5 \times \text{ULN}$  for AST, ALT and  $\leq 1.5 \times \text{ULN}$  for T. bilirubin unless liver metastases are present in which case LFT  $\leq 5 \times \text{ULN}$  for AST, ALT and T. bilirubin  $\leq 3.0 \times \text{ULN}$  prior to dosing.

If during the course of treatment abnormal LFT values are detected, the subject must be managed using the hepatotoxicity algorithm section of the ipilimumab Investigators.

## **5.6 Prohibited and Restricted Therapies During the Study**

### **Prohibited Therapies**

Patients in this study may not use vaccines for the treatment of cancer or prevention of disease unless indicated as a component of the protocol regimen (including those for common medical conditions) for up to one month pre- and post-dosing with ipilimumab. Concomitant systemic or local anti-cancer

medications or treatments are prohibited in this study while receiving ipilimumab treatments.

Patients may not use any of the following therapies during the study:

- Any non-study anti-cancer agent (investigational or non-investigational)
- Any other investigational agents
- Any other CTLA-4 inhibitors or agonists
- Anti PD-1 or anti PD-L1 antibodies
- CD137 agonists
- Immunosuppressive agents
- Chronic systemic corticosteroids
- Any non-oncology vaccine therapies used for the prevention of infectious diseases (for up to 30 days prior to or after any dose of study drug).

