#### **4.5 Early Withdrawal of Subjects**

##### **4.5.1 When and How to Withdraw Subjects**

Patients will be informed that they have the right to withdraw from the study at any time for any reason, without prejudice to their medical care. The investigator also has the right to withdraw patients from the study for any of the following reasons:

1. Intercurrent illness
2. Occurrence of an unacceptable adverse event
3. Patient request
4. Protocol violations
5. Non-compliance
6. Administrative reasons
7. Failure to return for follow-up

8. General or specific changes in the patient's condition unacceptable for further treatment in the judgment of the investigator

At the time of withdrawal, all study procedures outlined for the End of Study visit should be completed. The primary reason for a patient's withdrawal from the study is to be recorded in the source documents.

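### Section 5.6 prohibits immunosuppressive agents throughout the study with no toxicity exception, while Section 5.5 recommends two of them for steroid-refractory colitis

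*Combined protocol and SAP*

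**What the plan says.** Section 5.6 (Prohibited Therapies) introduces its list with "Patients may not use any of the following therapies during the study". Two entries matter here: "Immunosuppressive agents" and "Chronic systemic corticosteroids". Neither carries an exception for managing an adverse event, and the second does not say what makes a course chronic.

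Section 5.5 (Immune-mediated Enterocolitis) gives the management of a severe reaction: "Permanently discontinue ipilimumab in patients with severe enterocolitis and initiate systemic corticosteroids at a dose of 1 to 2 mg/kg/day of prednisone or equivalent". On improvement the instruction is to "initiate corticosteroid taper and continue to taper over at least one month". If steroids fail, it continues: "For steroid-refractory colitis infliximab 5 mg/kg IV or cyclosporine 2 mg/kg IV for 7 days are recommended". The hepatitis and dermatitis subsections also direct systemic corticosteroids, tapered over one month and at least one month respectively. Mycophenolate appears under hepatitis only as a report of past use.

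Section 4.5.1 lists the grounds on which the investigator has the right to withdraw a patient. One of them is "Protocol violations".

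**The concern.** The protocol gives two incompatible rules for the same patient at the same moment. One forbids a class of drug for as long as the patient is on study. The other recommends two members of that class when colitis does not respond to steroids. Staff treating a severe immune reaction should not have to decide which section of the protocol to break.

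There is a secondary matter of trial conduct. Nothing says that treatment given under Section 5.5 is not a protocol violation, and a violation is a listed ground for withdrawal. Whether such a patient stays in the study is therefore left to individual judgement.

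**Working it through.** **Do the two rules overlap in time?** The opening paragraph of Section 5.6 limits its ban on other anti-cancer treatment to the period of ipilimumab dosing. The list containing immunosuppressive agents is limited only by the duration of the study. Sections 3.1.2 and 6.1 keep patients on study until progression or death, and Section 3.1.4 follows those who stop ipilimumab until death or study closure. Stopping ipilimumab for severe enterocolitis therefore does not lift the ban, and the patient is still on study when infliximab or cyclosporine would be considered.

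**Is an exception implied?** Section 5.6 writes its limits out where it wants them: a one-month window for vaccines, and an allowance for vaccines that are part of the protocol regimen. It writes none for the immunosuppressive entry.

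**Is the steroid conflict equally clear?** No. Only chronic use is barred. Courses tapered over a month or more may or may not be chronic, and the text gives no way to tell. This is an ambiguity; the conflict over infliximab and cyclosporine is a direct contradiction.

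**How many patients could it touch?** Table 2 (Section 1.5.2) gives severe-to-fatal enterocolitis as 7% in both ipilimumab arms of the earlier phase 3 trial.

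- All severe enterocolitis: 32 × 0.07 = 2.24 patients expected.
- Steroid-refractory share *f*: not in the documents. With *f* as an assumption, the expected number is 2.24 × *f*: 0.56 at 25%, 1.12 at 50%, 2.24 at 100%.
- For comparison, any severe immune-mediated reaction is 12–15% in Table 2, or 32 × 0.12 = 3.84 to 32 × 0.15 = 4.8 patients. Most of these reactions are not enterocolitis that has failed steroids, so this is not the size of the clear conflict.

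These figures apply the rates for ipilimumab without SABR. Section 7.4 allows for the possibility that SABR doubles severe immune toxicity. If that applied to enterocolitis, the upper figure would be 32 × 0.14 = 4.48.

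**Does the conflict reach the primary analysis?** The design in Section 7.1 reproduces. With X the number progression-free and alive at 6 months among 32, P(X ≥ 8 | 0.15) = 0.096 and P(X ≥ 8 | 0.35) = 0.918, both within the 10% error limits. For a patient given a prohibited agent under Section 5.5:

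- Section 4.5.1 permits withdrawal but does not require it.
- Section 4.5.2 continues protocol visits for a withdrawn patient who agrees, and analyses data up to withdrawal for one who does not.
- Section 6.10 requires re-staging scans for patients who received SABR and ipilimumab, even if taken off protocol for adverse events after SABR. It also sets a scan at 6 months from enrollment.
- Sections 7.2 and 7.3 define the primary population by treatment received, with no exclusion for a protocol violation.

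The remaining route to a missing outcome is a withdrawn patient who declines further follow-up. As an illustration only, suppose *k* of the 32 have no 6-month status, count as failures, and would otherwise have had the 35% rate. Power is then P(X ≥ 8) among 32 − *k*: 0.918 at *k* = 0, 0.899 at *k* = 1, 0.876 at *k* = 2. Nothing in the documents supports a particular value of *k* arising from Section 5.6.

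**The case against.** The strongest reply is that the protocol plainly foresees immunosuppression for toxicity, so the Section 5.6 list must mean elective use. The evidence is fair. Section 5.4 makes failure to reduce the steroid dose to a stated level a reason to stop ipilimumab, and bars restarting ipilimumab while on systemic steroids apart from stable hormone replacement. Section 5.5 says steroid therapy should be individualized. This carries weight for steroids and is why that part is called ambiguous. It does not rescue the immunosuppressive entry, which is unqualified, runs for the whole study, and names the class to which the two agents recommended in Section 5.5 belong.

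A reader might infer the stronger point that patients managed under Section 5.5 are removed from the study, have no 6-month scan, and so bias the primary result through outcome-related loss. The documents do not support this. Withdrawal for a violation is discretionary, and Sections 3.1.4, 4.5.2, 6.10, 7.2 and 7.3 largely keep these patients in follow-up, imaging and the denominator. Section 5.6 also adds little to the withdrawal risk. Section 4.5.1 already lists an unacceptable adverse event, and Section 5.4 requires withdrawal when an adverse event makes continued therapy not in the patient's interest.

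Some gaps in toxicity-related follow-up are real. Section 3.1.4 leaves efficacy assessment after stopping for toxicity to standard of care, which sits uneasily with Section 6.10. Section 7.2 has no rule for a missing 6-month scan. Patients whose toxicity prevents SABR need no re-imaging and leave the denominator. None of these comes from the conflict between Sections 5.5 and 5.6, and editing Section 5.6 would not close them.

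**Conclusion.** Wrong as written. Sections 5.5 and 5.6 contradict each other on infliximab and cyclosporine for steroid-refractory colitis, and leave open whether month-long steroid courses are permitted. The case for correction is patient safety and does not depend on any effect on the primary endpoint.

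The clear conflict affects a subset of about 2.2 expected patients in 32. This assumes that the 7% rate of severe enterocolitis from the earlier trial carries over; the steroid-refractory share of those patients is unknown. Selective loss of outcomes through Section 5.6 is not shown. The residual statistical risk is confined to a patient who is withdrawn for the violation and then declines follow-up.

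**What to change.** Three edits are needed:

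- **Sections 5.5 and 5.6:** reconcile them so that the prohibited list and the toxicity-management text agree. Which clinical rule should prevail is for the investigators and sponsor, and this review does not choose.
- **Section 5.6:** define chronic for systemic corticosteroids, so that the status of the courses directed in Section 5.5 can be read from the text.
- **Section 4.5.1:** state whether treatment given under Section 5.5 counts as a protocol violation. State also that receiving it does not by itself end study follow-up or the 6-month scan, consistent with Sections 4.5.2 and 6.10.

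The cost is a few sentences in the next amendment. No visits or scans are added, and the 32 patients and the 8-of-32 rule are unchanged.

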### **Precautions**

Caution is advised when considering treatment with high-dose IL-2 in patients who have previously been administered ipilimumab, particularly in patients who experienced ipilimumab-related diarrhea/colitis. Colonoscopy or sigmoidoscopy with biopsy may be advisable prior to IL-2 administration once the patient is no longer receiving ipilimumab.

## **5.7 Method for Assigning Subjects to Treatment Groups**

This is an open label phase 2 study. There is no randomization. Patients will all receive ipilimumab 3 mg/kg for 4 doses 3 weeks apart. Between the second and third dose SABR will be used to oligometastatic sites.

## **5.8 Subject Compliance Monitoring**

Records of study medication used, dosages administered, and intervals between visits will be recorded during the study. The radiation treatment record will be reviewed and recorded.

## **5.9 Prior and Concomitant Therapy**

No other concomitant chemotherapy or systemic anti-melanoma therapy is allowed for the study.

## **6.0 STUDY PROCEDURES**

### **6.1 Treatment overview**

We will evaluate the combination of ipilimumab and SABR in patients with oligometastatic melanoma in this phase II trial.

The study will consist of the following schedule: ipilimumab will be administered on week 1 at a dose of 3 mg/kg.

Subsequent cycles of ipilimumab will be given every three weeks (week 4, 7, & 10).

SABR will be delivered between the second and third doses of ipilimumab (week 5-6) using the following suggested schedules: 18 Gy x 3 to lung, 10 Gy x 5 to liver, 6 Gy x 6 to nodal stations, 12 Gy x 3 to adrenal, 18 Gy x 1 to bone, and 24 Gy x 1, 18 Gy x 1, 15 Gy x 1 to < 2.0 cm, 2.0-3.0 cm, and >3 cm brain metastases, respectively.

Duration of therapy: Patients will receive at least 12 weeks of therapy and will be observed for toxicity for 90 days after the last ipilimumab infusion. Patients will remain on study until evidence of progression or death. Patients who meet criteria for reinduction therapy remain on study and re-induction is recommended if the criteria in Section 3.1.3 are met.

### **6.2 Screening**

Within four weeks of starting treatment, patients will have baseline hematologic studies including complete blood count plus differential, blood chemistry studies including chemistries, hepatic and renal function tests, thyroid and ACTH levels and a pregnancy test. Women of childbearing potential will have a pregnancy test within 3 days of starting treatment.

Within four weeks of starting treatment, patients will have CT of the chest, abdomen, and pelvis and/or PET/CT scan.

### **6.3. Stereotactic Ablative Radiation Therapy**

#### **6.3.1 Radiation Therapy**

SABR has now been formally defined and described in a published guideline from the American College of Radiology and American Society for Therapeutic

Radiology and Oncology. This protocol will respect that guideline. The term stereotactic for the purposes of this protocol implies the targeting, planning, and directing of therapy using beams of radiation along any trajectory in 3-D space toward a target of known 3-D coordinates. The coordinate system is defined by reliable “fiducial” markers. This differs from conventional radiation therapy, in which therapy is directed toward less-than-reliable skin marks or bony landmarks that are indirectly referenced to the tumor (surrogates). This protocol will require treatments to be conducted with the use of a fixed 3-D coordinate system defined by fiducials. The coordinate system defined by the fiducials should be directly related to the radiation-producing device (e.g., couch and gantry) in a reproducible and secure fashion. Capability should exist to define the position of targets within the patient according to this same 3-D coordinate system. As such, the patient is set up for each treatment with the intention of directing the radiation toward an isocenter or target according to the known 3-D coordinates as determined in the process of treatment planning. The nature of the fiducials themselves may include radiopaque markers or rods placed at known locations in a frame or fixed structure adjacent to the patient as well as use of the tumor itself as a fiducial (e.g., acquiring tomographic views of the tumor simultaneously with the treatment). Metallic “seeds” placed within the tumor will be allowed to constitute a fiducial so long as the methods are validated and a plan is in place to identify seed migration (e.g., redundant seeds placed).

### 6.3.2 Fractionation, Total Dose and Radiation Therapy Planning

Megavoltage external beam photon radiation therapy will be used delivered by a linear accelerator generating 6 MV photons or in the case of SRS to the brain a Gamma Knife. A CT simulation or MR simulation will be used for radiation therapy planning. During simulation where appropriate a 4-D CT should be used to determine the motion of targeted metastases with respiration. Efforts to limit respiratory motion such as gated treatment, Active Breath Control systems, or abdominal compression should be used in order to minimize necessary GTV to ITV expansions.

### 6.3.3 Field Definition

Gross tumor volume (GTV) is defined as the full extent of the imaging abnormality.

ITV is defined as the GTV plus margin needed to account for physiologic motion as determined by the data acquired at the time of 4-D CT.

Clinical target volume (CTV) equals ITV in SABR.

The planning target volume (PTV1) includes the CTV plus a 0.5 cm margin for set-up error and/or patient motion. Exact margins will be left to the discretion of the treating radiation oncologist.

### 6.3.4 Dose Considerations

Lung SABR recommended doses: 18 Gy x 3 to peripheral lung masses, 10 Gy x 5 to central lung masses given 2 fractions per week

Liver SABR recommended doses: 10 Gy x 5 given 2-3 fractions per week

Nodal station SABR recommended doses: 6 Gy x 6 given 3 fractions per week

Adrenal SABR recommended doses: 12 Gy x 3,

Vertebral body SABR recommended doses: 16-18 Gy x 1 respecting normal tissue spinal cord constraints particularly no more than 10 Gy to 10% of cord volume

Brain parenchymal SABR recommended doses: 24 Gy x 1, 18 Gy x 1, 15 Gy x 1 to < 2.0 cm, 2.0-3.0 cm, and >3 cm brain metastases, respectively dosed to the 50-70% isodose line if using Gamma Knife SRS.

Fractionation: Treatment shall be given 2-3 days per week at the treating radiation oncologist's discretion.

Dose Homogeneity: The dose throughout the treatment volume will be within 10% of the prescribed dose. Wedges, compensation, and other methods of generating a uniform dose distribution are encouraged. IMRT can be used to shape dose around critical normal structures.

Isodose Plans: The isodose distribution for the composite plan shall be calculated. The prescription point and the outline of the tumor volume shall be shown.

Image guidance: Pre-treatment kilovoltage on board CT imaging will be done for localization, and shifts will be made as appropriate per the treating radiation oncologist.

Treatment Modification: Uninterrupted treatment is planned, and SABR fractions should occur during the period between the 2nd and 3rd doses of ipilimumab (generally weeks 5-6). SABR can be delayed at the physician's discretion if there is concern for overlapping toxicities with ipilimumab, but SABR should always be delivered between infusion 2 and infusion 3 of ipilimumab. The entire course of SABR should be delivered within the 3 week period between ipilimumab infusions, except in the case of a grade 3+ toxicity in the middle of the course of SABR. If a grade 3+ toxicity occurs during SABR which interrupts the delivery of SABR, then the final SABR fractions will be delivered after the toxicity returns to grade or lower with appropriate supportive care measures.

On Treatment Management: The patient will be examined at least once a week during the course of radiation therapy.

